9.4 Data Sources

Data will be collected retrospectively from charts of patients treated previously with HES 130. Data entry based on patient charts will be performed by investigator and/or delegated qualified study staff at the participating HES-accredited hospital using the eCRF (for more details refer to [Section 9.3](#)).

[figure not shown]
The documentation process is defined as follows (see Figure 2):

- After accreditation of the hospital and once a reasonable number[§] of patients has been treated with HES 130 documentation period begins with the most recently treated eligible patient at the respective HES-accredited hospital.
- Further eligible patients will be documented chronologically backwards week by week until 8 weeks after initial accreditation of the hospital
- The order of patient documentation will be determined by the date of initial HES 130 infusion
- Overall study documentation will be stopped once the targeted number of patients for the study (see [Section 9.5](#)) is reached

All data will be pseudonymised.

[§] This will depend on the results of the feasibility survey.

Figure 2 Documentation Process

Note: Patients treated with HES 130 within the documentation period, but admitted to the hospital before the end of documentation period (i.e. within the 8-week period after hospital accreditation), are allowed to be documented. Documentation of data from patients treated with HES 130 before the end of the documentation period (within the 8-week period after accreditation of hospital) will not be allowed.

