9.2.1 Countries, Feasibility and Site Selection

Prior to the start of the DUS, a feasibility survey will be performed by the CRO. The feasibility check of HES-accredited hospitals intends to evaluate e.g.

- which wards of the hospitals have prescribed HES 130 products listed in Annex 1a/1b after HES accreditation
- whether patients had been treated with HES 130 within the documentation period (see [Section 9.4](#))
- the number of patients which have been prescribed with HES 130 by physicians of these wards
- whether the wards at the HES-accredited hospitals have the qualified resources to be compliant with the procedures of case assessment, data entry, and verification mentioned in this study protocol (see [Section 9.3](#) and [Section 9.8.1](#))
- whether the HES-accredited hospitals used electronic patient data management system (PDMS) or paper-based documentation within the documentation period (see [Section 9.4](#))
- whether the HES-accredited hospitals have a defined policy for collection of patient consent for using retrospective data for research projects
- whether the sites are willing to participate

Electronic PDMS allows a more convenient review of patient charts at the hospital regarding prescription of HES in the given retrospective data collection period compared to paper-based documentation. Hospitals which prescribed HES to a sufficient number of patients in the documentation period (see [Section 9.4](#)) will be preferred. The use of electronic PDMS will be considered secondary in the selection process and will not overrule the prescription frequency. Therefore, selection of hospitals with combined use of electronic PDMS and paper-based documentation or use of only paper-based documentation will be possible. The CRO will discuss the results of the feasibility survey with the sponsor.

The DUS is intended to be conducted in a representative sample of member states of the EU, e.g. Belgium, Czech Republic, France, Germany, Hungary, Italy, Poland, Spain, The Netherlands. Final country selection will be based on the results of the feasibility, countries with high non-adherence rates participating in the first HES DUSs (ENCePP Register)⁴, HES 130 sales figures and the willingness of HES-accredited hospitals to participate in this DUS.

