9.9 Limitations of the Research Methods

The following types of bias or limitations may occur in this retrospective, non-interventional DUS:

- Prescription behaviour of physicians might be influenced by the preceding feasibility survey
- Number of HES-accredited sites/hospitals and physicians willing to participate in the conduct of this DUS might be limited, i.e. the number of participating sites/hospitals might be not representative, and the intended sample size might not be reached in the documentation period
- Incomplete/implausible data in the individual patients' original medical records may not be possible to be clarified and/or remain not assessable
- Due to retrospective design determination of indication (e.g. acute blood loss) and contraindications (e.g. dehydration) might not be clearly possible based on patients' charts of already treated patients. Such cases will remain not assessable
- For contraindications such as severe hypernatraemia, severe coagulopathy, and severely impaired hepatic function mentioned in the EU HES PIs there are no generally accepted/established definitions which are uniformly used by different hospitals or physicians. Evaluation of contraindications based on post-hoc definitions in the context of a retrospective DUS will not necessarily match current local guidelines and the patient assessment of the prescribing physician at the time of patient treatment (e.g. a prescribing physician assessed the patient as having no severely impaired coagulation, while the post-hoc definition provided in Annex 2 categorises the patient as having severe coagulopathy, i.e. false-positive non-adherence)
- Source data verification of the data by the CRO/sponsor by reviewing the individual patients' original medical records will not be possible. However, data entered in the eCRF regarding indication and contraindication should be verified by applying the four-eyes principle ([Section 9.8.1](#))

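### Section 9.4 sets no cut-off or flag at the feasibility-survey contact, so patients treated after a contact that Section 9.9 says might affect prescribing enter the primary proportion unmarked

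*Protocol*

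**What the plan says.** Section 9.2.1 places the survey first: "Prior to the start of the DUS, a feasibility survey will be performed by the CRO". Among other things it asks "which wards of the hospitals have prescribed HES 130 products listed in Annex 1a/1b after HES accreditation", how many patients were prescribed HES 130, and whether the site will take part.

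Section 9.4 sets the sampling rule. Once a sufficient number of patients has been treated, the "documentation period begins with the most recently treated eligible patient at the respective HES-accredited hospital". A footnote on that number says: "This will depend on the results of the feasibility survey". The rule continues: "Further eligible patients will be documented chronologically backwards week by week until 8 weeks after initial accreditation of the hospital". On sequence: "The order of patient documentation will be determined by the date of initial HES 130 infusion". On stopping: "Overall study documentation will be stopped once the targeted number of patients for the study" is reached. Section 9.5 sets that number at 1749, with a fallback of 1220.

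The inclusion criterion in Section 9.2.3 requires treatment after the risk minimisation measures and within the documentation period. It adds no upper limit of its own.

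The first limitation in Section 9.9 reads: "Prescription behaviour of physicians might be influenced by the preceding feasibility survey".

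**The concern.** The primary proportion is meant to show how HES 130 is used in routine practice after the risk minimisation measures, and so whether those measures work (Sections 8 and 9.2.2). There is no comparator. If contact with the study changes prescribing, that change is mixed into the same proportion and cannot be told apart from the effect of the measures.

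A retrospective chart review can usually avoid this problem, because care given before anyone was approached cannot have been affected by the approach. Section 9.7.2 relies on the retrospective design to reduce bias. Care given between survey contact and the opening of documentation does not have that protection. Sampling begins at exactly that end of the calendar, and the plan does not mark where the protection ends.

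**Working it through.** **1. Order of events.** The footnote in Section 9.4 makes the start of documentation depend on the survey results, so documentation opens after the survey. Section 6 lists hospital selection and contract negotiations among the things that determine the start of data collection. An interval between contact and documentation is therefore expected. Its length is not stated.

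**2. Upper limit.** Sections 9.2.3 and 9.4 give a lower time bound (8 weeks after accreditation) and no upper one at the survey. The four sensitivity analyses in Section 9.7.1 deal with inconclusive indication and missing contraindication values. None separates patients by date of contact.

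**3. The plan's precision, reproduced.** The exact two-sided 95% Clopper-Pearson interval at a rate of 50% has a width of 5.001 points for n = 1573 and 4.9998 points for n = 1574. Then 1574 / 0.9 = 1748.9, rounded up to 1749. For a width of 6 points the minimum is n = 1098 (5.999 points), and 1098 / 0.9 = 1220. Both stated sizes are correct. The planned half-width is at most 2.5 points, or 3 points under the fallback.

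**4. What share could be post-contact?** This rests on assumptions. From the Commission decision (17 Jul 2018) to the planned start of data collection (31 Oct 2019) is 471 days, or 67.3 weeks. Subtracting the 8 excluded weeks leaves at most 59.3 weeks for a hospital that starts documenting on that date. With even use over time and every eligible patient documented, contact 8, 13 or 26 weeks earlier gives shares of:

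- 8 / 59.3 = 13%
- 13 / 59.3 = 22%
- 26 / 59.3 = 44%

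Later accreditation shortens the window and raises these shares. So does a stop at target: if it leaves only the most recent 30 weeks, 13 weeks of post-contact time becomes 13 / 30 = 43% instead of 22%.

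**5. Possible shift in the primary rate.** Shift = post-contact share × change in rate among those patients. Both inputs are assumed.

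| Share | 5-point change | 10-point change |
|---|---|---|
| 25% | 1.25 | 2.5 |
| 50% | 2.5 | 5.0 |

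A fixed 10-point fall is impossible at the lowest rate considered in Section 9.5 (5%), so a relative version is a useful check: shift = share × rate × (1 − ratio). With an assumed rate of 30% and a post-to-pre ratio of 0.75, the shift is 0.25 × 30 × 0.25 = 1.9 points at a 25% share and 3.8 points at a 50% share. With a ratio of 0.9 it is 0.8 and 1.5 points. A larger sample does not reduce any of these figures.

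**The case against.** The strongest reply is that the plan openly lists survey influence as a limitation and states nothing false. That is fair. The point is that it leaves a named influence without a marker when the dates needed for one are nearly all collected.

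A reader might infer more, and four stronger readings do not hold:

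- **That the backward order itself causes the bias.** Order changes who is sampled only if 1749 is reached before hospitals run out of patients. Sections 9.5 and 9.9 both allow that it may not be. In that case, with full documentation, every eligible patient enters whatever the order, and only the missing cut-off or flag remains.
- **That the earliest patients are the clean ones.** They are closest to accreditation and training. Any waning of the training effect would show in later patients, so moving the sample earlier could itself raise measured adherence.
- **That the bias favours the sponsors.** Section 9.9 says the survey might influence behaviour and gives no direction. Better adherence after contact is plausible, but the documents do not say who answers the survey or whether prescribers learn that their adherence will be judged.
- **That the rate is off by up to the full interval width.** The 5.0-point figure needs both upper assumptions together. The other three combinations give at most 2.5 points.

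Two further cautions stand. Section 9.2.1 has the survey ask about the documentation period in the past tense, which may suggest a period largely over by then. Figure 2 is not available here and could show an upper bound. The affected share at a given hospital could therefore be small or nil. Section 9.7.1 also leaves analytic detail to the SAP, so the split could be specified there.

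**Conclusion.** The point holds in limited form. On the readable text, patients treated after survey contact enter the primary proportion with nothing to identify them, although the plan says that contact might change prescribing. Where the stop at 1749 takes effect, they are also over-represented.

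The size and direction of any bias cannot be determined from the documents. The shift of 1.25 to 5.0 points rests on an assumed 25% to 50% share and an assumed 5 to 10 point change. It shows only that an effect comparable to or larger than the planned half-width is possible. The sample size is unaffected. The documents do not support saying that the study is biased in the sponsors' favour, or that the backward order is wrong in itself.

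**What to change.** Record, for each hospital, the date of the CRO's first study contact. Flag every patient whose first HES 130 infusion falls on or after that date. Report the primary variable with and without the flagged patients as a stated sensitivity analysis. Section 9.3 already collects the full date and time of each bag, so the added cost is one date per hospital and one table. No patient's inclusion changes. The analysis without flagged patients is less precise: at a rate of 50%, with width scaling as 1/√n, removing 25% of 1574 gives about 5.0 / √0.75 = 5.8 points, and removing 50% gives about 5.0 / √0.5 = 7.1 points.

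Optionally, start the backward documentation at the last pre-contact patient and use post-contact patients only to reach the target. This is a trade-off: late-accredited hospitals have fewer pre-contact patients, the sample moves closer to accreditation training, and the change may count as a substantial amendment needing PRAC approval under Section 10.2.

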9.5 Study Size

The sample size calculation is based on the primary statistical unit of the study: Patients treated with HES 130.

For potential non-adherence rates of 5 % to 95 % and aiming for a precision (defined as the confidence interval width) of up to 5 percent points of the exact two-sided 95 % confidence interval (according to Clopper-Pearson) for the evaluation of non-adherence, a sample size of 1574 patients is required. To compensate for potential cases where the indication for use has been assessed as “not possible to conclude due to retrospective design” or missing data regarding posology (assumption of 10 %), 1749 patients will be documented.

In case the intended targeted sample size of 1749 could not be reached in the documentation period, analysis with a sample size of 1220 (including 10 % compensation for cases assessed as “not possible to conclude due to retrospective design” or missing data regarding posology) will be performed to ensure a precision (confidence interval width) of at least 6 percent points.

However, the sponsor will make any effort to reach the intended target sample size of 1749.

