9.7 Data Analysis

9.7.1 Methods

Due to the exploratory character of this study only descriptive statistics will be used for the analysis of the variables listed in [Section 9.3](#). For continuous variables, mean \pm standard deviation, median and quartile (25th; 75th percentile) and numbers of non-missing and missing values will be presented. For categorical variables, frequencies and percentage will be shown for each category and for missing values.

Primary Variable

To assess the non-adherence of hospital physicians to the approved European PIs of HES 130 solutions (see Annex 1a/1b), the primary variable will be the number and proportion of patients whose treatment during the hospital stay did not adhere to the approved European PIs regarding indication, contraindications and dosage (posology)**. The full analysis set will comprise all eligible patients.

The number and percentage of patients who received HES 130 and were documented as non-adherent to one or more of the specifications made in the PIs (concerning the indication, contraindications and dosage) will be evaluated for the overall patient population and will be displayed together with 95 % confidence intervals for the percentage.

For the primary analysis, missing data regarding indication and posology (dosage) will neither be defined as non-adherent nor adherent prescription; this also applies if “not possible to conclude due to retrospective design” is assessed regarding indication. If more than one HES 130 prescription is reported for the same patient, every single prescription needs to adhere to the approved European PIs for counting the patient's total HES 130 treatment as adherent. That means, if at least one prescription will be non-adherent, the patient's total HES 130 treatment will be counted as non-adherent (see also Figure 3 and Figure 4 below).

Sensitivity Analyses of the Primary Variable

In addition, sensitivity analyses of the primary variable will be conducted in which “not possible to conclude due to retrospective design” regarding indication will be evaluated as

- non-adherent prescription (sensitivity analysis 1)
- adherent prescription (sensitivity analysis 2)

** Infusion of HES 130 for > 24 hours is considered as off-label use. Infusion of > 30 ml/kg for 24 hours of HES 130 (6 %) and > 18 ml/kg of HES 130 (10 %) for 24 hours is considered as off-label use.

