Furthermore, sensitivity analyses regarding the contraindications of special interest (critically ill, sepsis, renal impairment)[#] will be done. For these, missing values will be evaluated as

- non-adherent prescription (sensitivity analysis 3)
- adherent prescription (sensitivity analysis 4)

Further Analyses

Similar to the analysis of the primary variable, non-adherence to individual specifications made in the PIs will be evaluated (i.e. HES 130 use outside indication, presence of any contraindication at the start time of HES 130 infusion, presence of contraindications at the start time of HES 130 infusion by each type of contraindication and dosage outside the specifications made in the PIs).

Additionally, the number and percentage of patients whose treatment during the hospital stay does not adhere to one or more specifications made in the approved European PIs [concerning the indication, contraindications and dosage (posology)] will also be evaluated for each country.

[figure not shown]
Furthermore, analysis of non-adherence to one or more specifications made in the approved European PIs (concerning the indication, contraindications and dosage [posology]) will also be conducted for each single HES 130 prescription as statistical unit for assessment (instead of considering the patient as statistical unit) and will be presented as secondary measure.

For this purpose, each prescription is defined as a treatment with a single or multiple HES 130 infusion(s) in a row until a change of the following occurred (see also Figure 1 above):

- Indication at start time of HES 130 infusion OR
- Trade name OR
- Prescribing physician OR
- Main medical procedure at start time of HES 130 infusion OR
- The subsequent HES 130 infusion was interrupted from the previous HES 130 infusion by a HES-free interval of ≥ 24 h (see example in Figure 3). To minimise calculation errors by the sites this definition will be applied technically (and is therefore not defined in [Section 9.3](#), Figure 1).

[figure not shown]
[#] Main focus of PRAC

Figure 3 Example A for Prescription

In case the treatment duration (including HES-free interval(s) of < 24 h) exceeded 24 h and comprised several single prescriptions as defined above, only prescriptions exceeding the 24 h period will be regarded as non-adherent (see example in Figure 4 prescriptions 3 and 4).

Figure 4 Example B for Prescription

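### The 5-point and 6-point precision figures in section 9.5 hold only if patients are independent, but patients are documented within hospitals and no allowance for this is made

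*Protocol*

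**What the plan says.** Section 9.5 of the protocol takes the patient as the unit: "The sample size calculation is based on the primary statistical unit of the study: Patients treated with HES 130". It covers a wide range of rates ("For potential non-adherence rates of 5 % to 95" %), sets the target by "aiming for a precision (defined as the confidence interval width) of up to 5 percent points of the exact two-sided 95 % confidence interval", and names the method ("according to Clopper-Pearson) for the evaluation of non-adherence"). From this, "a sample size of 1574 patients is required". A 10% allowance for inconclusive indication or missing posology raises the number documented to 1749. If that is not reached, 1220 documented patients are to give 6 points.

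Section 9.7.1 says that the overall primary percentage "will be displayed together with 95 % confidence intervals for the percentage". It names no interval method there and does not mention hospital.

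The sampling is described elsewhere. Hospitals are chosen on feasibility, prescribing volume and willingness to take part (9.2.1). Within each hospital, patients are documented consecutively (9.2.2), from the most recent backwards to 8 weeks after accreditation (9.4). "Overall study documentation will be stopped once the targeted number of patients for the study" is reached, which is a study-wide rule; no limit or expected number per hospital is given. Indication and contraindications are assessed at the site, and the local principal investigator settles unresolved discrepancies (9.3, 9.6.2, 9.8.1). The rationale in 9.1 is a reliable record of non-adherence in the EU.

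**The concern.** Clopper-Pearson is exact for independent binomial observations. Here the patients come in groups. Patients of one hospital share prescribers, the hospital's accreditation and training, and the same local assessors. The outcome is prescriber behaviour as judged by those assessors, so patients of one hospital should resemble each other more than patients of different hospitals. The protocol itself expects rates to differ between places, since it selects countries partly on earlier high non-adherence (9.2.1).

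The inference is meant to reach beyond the participating hospitals, so between-hospital variation belongs in the interval. Left out, it makes the rate look more precisely known than it is. Precision is the only criterion behind both 1749 and 1220, and the result goes to the regulator to judge whether the risk minimisation measures work.

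**Working it through.** **Inputs from the protocol (9.5):** 95% Clopper-Pearson interval; width at most 5 points (fallback 6); rates 5% to 95%; 10% allowance; 1574 evaluable and 1749 documented; fallback 1220 documented.

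**Inputs assumed, because the protocol gives neither:** number of hospitals k and ICC. Hospitals are taken as equal in size.

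**Step 1: reproduce the stated figures under independence.** The maximum Clopper-Pearson width over all possible counts is:
- n = 1573: 5.0014 points; n = 1574: 4.9998 points. So 1574 is the smallest n that meets 5 points.
- n = 1098: 5.9992 points, which meets 6 points.
- 1574/0.9 = 1748.9, rounded up to 1749; 1098/0.9 = 1220.

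The arithmetic is correct, and there is no reserve at the worst-case rate of 50%.

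**Step 2: allow for hospitals.** With m = 1574/k patients per hospital, the design effect is DE = 1 + (m − 1) × ICC and the effective sample size is 1574/DE. The width is Clopper-Pearson at the effective size. The approximate coverage of the unadjusted interval is 2Φ(1.96/√DE) − 1.

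Worked case, k = 40 and ICC 0.05: m = 1574/40 = 39.35; DE = 1 + 38.35 × 0.05 = 2.92; effective n = 1574/2.92, about 540; width at a 50% rate 8.6 points; coverage 2Φ(1.96/1.708) − 1, about 75%.

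| Hospitals | ICC | DE | Width at 50% rate (points) | Coverage of unadjusted interval |
|---|---|---|---|---|
| 100 | 0.01 | 1.15 | 5.4 | 93% |
| 100 | 0.05 | 1.74 | 6.6 | 86% |
| 40 | 0.02 | 1.77 | 6.7 | 86% |
| 40 | 0.05 | 2.92 | 8.6 | 75% |
| 40 | 0.10 | 4.84 | 11.1 | 63% |
| 20 | 0.05 | 4.88 | 11.2 | 63% |
| 20 | 0.10 | 8.77 | 15.1 | 49% |

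For the fallback with 40 hospitals and ICC 0.05: m = 1098/40 = 27.45; DE = 1 + 26.45 × 0.05 = 2.32; effective n about 473; width at 50% about 9.2 points instead of 6.

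**Step 3: rates away from 50%.** The largest design effect that still keeps the width within 5 points at n = 1574 is about 1.04 at a 40% rate, 1.18 at 30%, 1.54 at 20%, 2.65 at 10% and 4.71 at 5%. The same values apply to the mirrored high rates. With 40 hospitals and a 10% rate, the width is about 4.1 points at ICC 0.02, 5.2 at 0.05 and 6.8 at 0.10. The coverage column does not depend on the rate in this approximation.

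**The case against.** The strongest objections, and what stands of each:

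- **The size of the shortfall is assumed.** This stands. Neither the number of hospitals nor the ICC is in the protocol, so no single figure can be called the true width. A reader might infer that 5 points will certainly be missed whatever the rate. The documents do not support that: at rates near 5% to 10%, or 90% to 95%, moderate clustering can leave the width within target. What fails under any positive ICC is the promise over the whole range, because nothing is in reserve at 50%.
- **The analysis may be settled in the SAP.** This stands in part. Section 9.7.1 names no method and defers details to a SAP, which was not available for this review. A clustered interval there would repair coverage. It would not repair the precision statement fixed in 9.5, which names Clopper-Pearson for evaluating non-adherence.
- **The study is exploratory and descriptive.** There is no test or success threshold for a wider interval to overturn, and using a clustered interval need not alter the pooled percentage. That limits the consequence, but the interval remains the stated measure of precision.
- **Hospitals are not a random sample.** True: a design-effect correction does not cure selection. Section 9.9 admits that sites may be unrepresentative, but does not mention clustering.

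A reader might also infer that the country, subgroup and prescription-level results need nested intervals. Section 9.7.1 expressly promises an interval only for the overall patient population, so that demand goes beyond the text. Nor does the point require a cap on patients per hospital: a clustered interval can handle unequal sizes, and a cap would cut across the backward documentation rule in 9.4 and worsen the recruitment risk noted in 9.9.

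**Conclusion.** The point holds for the unconditional precision claim in 9.5 and for the overall primary interval if it is computed by the method named there. The sample-size arithmetic is right; the independence behind it does not fit the sampling described in 9.2 and 9.4 or the EU-wide aim in 9.1.

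At a 50% rate, the likely width runs from just above 5 points in a favourable case to about 15 points with few hospitals and strong correlation. This rests on assumed hospital numbers of 20 to 100, ICC of 0.01 to 0.10 and equal hospital sizes; unequal sizes would widen it further. Whenever the ICC is positive, the unadjusted interval is too narrow at every rate, even where the adjusted width still meets the target.

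**What to change.** 1. In 9.5, state that 1574 evaluable (1749 documented) and 1098 evaluable (1220 documented) give 5 and 6 points only under independence. Add a short table of expected widths over a stated range of ICC, number of hospitals and non-adherence rates. The feasibility survey can inform the number of hospitals.
2. In 9.7.1, specify that the 95% interval for the overall primary proportion takes hospital as the cluster, for example Clopper-Pearson at the design-effect-adjusted effective sample size, or a cluster-robust logit interval.

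The cost is wording, a less favourable precision figure and a wider reported interval. Hospital identity is already recorded in the eCRF (9.3), so no new data and no extra patients are needed.
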